3.5 Sample Size Considerations

The proposed Phase 2 study will have a sample size that would likely detect a 50% reduction from baseline in seizure frequency compared to placebo. Such a treatment effect would be greater than or equal to that demonstrated by many of the approved AEDs for refractory epilepsy, such as lamotrigine, oxcarbazepine and levetiracetam ([Glauser et al. 2000](#)), ([Glauser et al. 2006](#)), ([Trevathan et al. 2006](#)). A theoretical treatment effect of this magnitude, in light of the benign safety profile of UX007 shown to date, is considered to be clinically meaningful by physician experts. From the perspective of accurately determining seizure frequency, the proposed durations are deemed sufficient and are accounted for in the standard deviation (55%) used in the power calculation.

For the study to be adequately powered, a sample of approximately 40 completed subjects was estimated to be adequate to detect a 50% between-group difference in seizure frequency per 4 weeks with power of approximately 80% and population standard deviation of 55% using two-sample t test at one-sided alpha level of 0.05.

3.6 Primary Analyses

Evaluations will occur at the following key time points:

- **Primary Analysis:** The primary, week 8, analysis will occur when all subjects have completed the 8 week double-blind placebo-controlled treatment period, or withdrawn from the study prior to the week 8 visit.
- **Final Analysis:** The final analysis will occur when all subjects have completed the open-label extension period, or withdrawn from the study.

3.7 Data Monitoring Committee

A DMC with appropriate expertise in the conduct of clinical trials in children will act in an advisory capacity to monitor subject safety on a routine basis throughout the trial. The DMC will also monitor individual subject tolerability and implement individual subject stopping criteria based on the National Cancer Institute Common Terminology Criteria for Adverse Events (NCI-CTCAE), Version 4.0. The DMC will be consulted for the management of individual subjects who experience unacceptable tolerability issues (such as significant gastrointestinal distress). The DMC may:

- Review the study protocol and informed consent documents, and plans for data monitoring
- Evaluate the progress of the trial, study data quality, timeliness, subject recruitment, accrual and retention, subjects' risk versus potential benefit, and other factors that could affect the study outcome
- Consider relevant information that may have an impact on the safety of the participants or the ethics of the study
- Make other recommendations to Ultragenyx concerning continuation, termination or other modifications of the study based on their observations of the study.

The detailed roles and responsibilities of the DMC are specified in the DMC Charter.

4 STUDY ENDPOINTS, COVARIATES AND SUBGROUPS

The clinical efficacy tests / instruments evaluated in this study are summarized in [Table 1](#). See the study protocol for the detailed description of each test.

Table 1: Study Outcomes

Seizure Frequency and Response

- Observable seizures measured by seizure diary [**]
- Absence seizures measured by overnight electroencephalogram (EEG) [**]

Movement

- Movement ability measured by 6-minute Walk Test (6MWT) [*]
- Paroxysmal exertional dyskinesia (PED) events measured by 6MWT [*]
- Gross motor function measured by Gross Motor Function Measure-88 (GMFM 88) [*][#]
- Gait analysis measured during 6MWT [#]

Neurological Function

- Neuropsychological function measured by Computerized Neuropsychological Test - Cambridge Neuropsychological Test Automated Battery (CANTAB) [*]
- Physical neurological findings measured by Columbia Neurological Score (CNS)
- Global impression of disease improvement measured by Clinical Global Impression –Improvement (CGI-I)
- Receptive vocabulary achievement and verbal ability measured by Peabody Picture Vocabulary Test (PPVT) [#]
- Visual and motor coordination measured by Beery-Buktenica Developmental Test of Visual Motor Integration (Beery-VMI) [#]
- Spatial understanding and abstract reasoning measured by Raven’s Coloured Progressive Matrices (RCPM) [#]

Quality of Life

- Physical and psychosocial health-related quality of life measured by Short Form-10 (SF-10) Health Survey in subjects under 18 years of age
- Physical and psychosocial health-related quality of life measured by Short Form-12 (SF-12) Health Survey in subjects 18 years of age and over
- Functional capabilities and performance measured by Pediatric Evaluation of Disability Inventory Computer Adaptive Test (PEDI-CAT)[#]

[**] Primary efficacy measures

[*] Secondary efficacy measures

[#] Measured at select sites only

Each of the primary and secondary endpoints will be compared between the UX007 and placebo groups during the double-blind, placebo-controlled treatment period.

4.1 Primary Efficacy Endpoint

The primary endpoint to evaluate the efficacy of UX007 in Glut1 DS is as follows:

- Reduction from baseline to week 8 in frequency of seizures (normalized to a 4-week rate): observable seizures measured for 6 weeks after 2-week titration by diary and absence seizures measured overnight by electroencephalography (EEG). The primary efficacy endpoint will be derived for each subject based on subject seizure type at randomization: observable seizures from the diary will be used for Observable Seizures Subjects and absence seizures from EEG will be used for Absence Seizures Only Subjects (see Section 5.6).

4.2 Secondary Efficacy Endpoints

The following are considered secondary endpoints to evaluate the efficacy of UX007 in Glut1 DS:

- Reduction from baseline to week 8 in frequency of observable seizures (normalized to a 4-week rate) measured for 6 weeks after 2-week titration by diary
- Reduction from baseline to week 8 in frequency of absence seizures (normalized to a 4-week rate) measured overnight by EEG
- Seizure response at Week 8, defined as at least 50% reduction from baseline to week 8 in frequency of seizures
- Observable seizure response at Week 8, defined as at least 50% reduction from baseline to week 8 in frequency of observable seizures measured by diary
- Absence seizure response at Week 8, defined as at least 50% reduction from baseline to week 8 in frequency of absence seizures measured overnight by EEG
- Cognitive function using the Cambridge Neuropsychological Test Automated Battery (CANTAB): change from baseline to Week 8 in the following scores:
 - Reaction Time (RTI):
 - Simple Choice Median Reaction Time (RTIMDSRT)
 - Five Choice Median Reaction Time (RTIMDFRT)
 - Simple Choice Standard Deviation (RTISRTSD)
 - Spatial Span (SSP):
 - Span Length (SSPSLF)
 - Paired Associates Learning (PAL):
 - Total Errors (Adjusted) (PALTEA)
 - First Trial Memory Score (PALFTMS)

- Spatial Working Memory (SWM):
 - Between Errors (SWMBE48)
 - Strategy (SWMS68)
- Change from baseline to Week 8 in distance traveled (in meters) as measured by 6MWT
- Change from baseline to Week 8 in distance traveled (in percent predicted) as measured by 6MWT
- Time (in minutes) to onset of paroxysmal exertional dyskinesia (PED) as measured during 6MWT through Week 8
- Gross motor function using the Gross Motor Function Measure-88 (GMFM-88): change from baseline to Week 8 in Total Score.
- Reduction from baseline over time in frequency of seizures (normalized to a 4-week rate): observable seizures measured daily by diary and absence seizures measured overnight by electroencephalography (EEG)
- Reduction from baseline over time in frequency of observable seizures (normalized to a 4-week rate) measured daily by diary
- Reduction from baseline over time in frequency of absence seizures (normalized to a 4-week rate) measured overnight by EEG

4.3 Exploratory Efficacy Endpoints

The following are considered exploratory endpoints and provide supplemental information to evaluate the efficacy of UX007 in Glut1 DS:

- Cognitive function using the Cambridge Neuropsychological Test Automated Battery (CANTAB), change from baseline over time in the following scores: RTIMDSRT, RTIMDFRT, RTISRTSD, SSPSLF, PALTEA, PALFTMS, SWMBE48, SWMS68
- Change from baseline over time in distance traveled (in meters) as measured by 6MWT
- Change from baseline over time in distance traveled (in percent predicted) as measured by 6MWT
- Time (in minutes) to onset of paroxysmal exertional dyskinesia (PED) as measured during 6MWT over time
- Gross motor function using the Gross Motor Function Measure-88 (GMFM-88): change from baseline over time in the following scores: Lying and Rolling; Sitting; Crawling and Kneeling; Standing; Walking, Running and Jumping; Total Score
- Change from baseline in Neurological function using the Columbia Neurological Score (CNS) total score
- Physician global impression of change in clinical status ([Guy 1976](#))

- Clinical Global Impression - Improvement scale (CGI-I)
- Change from baseline in Receptive vocabulary using the Peabody Picture Vocabulary Test (PPVT) standardized score
- Subject or caregiver-reported quality of life using Short Form-10™ (SF-10) Health Survey for children (subjects 5 through 17 years of age): change from baseline in two component summary T-scores:
 - Physical Summary Score (PHS-10)
 - Psychosocial Summary Score (PSS-10)
- Subject or caregiver-reported quality of life using Short Form-12v2 (SF-12v2) Health Survey for adults (subjects 18 years of age and older): change from baseline in 8 domain norm based scores and two component T-scores:
 - Physical Functioning (PF)
 - Role Limitations due to Physical Health (RP)
 - Bodily Pain (BP)
 - General Health Perceptions (GH)
 - Vitality (VT)
 - Social Functioning (SF)
 - Role Limitations due to Emotions Problems (RE)
 - Mental Health (MH)
 - Physical Component Summary Scale (PCS-12)
 - Mental Component Summary Scale (MCS-12)
- Functional disability by caregiver report using the Pediatric Evaluation of Disability Inventory – Computer Adaptive Test (PEDI-CAT) for all subjects under the age of 18 (or for subjects 18- 20 years as clinically indicated) at the time of informed consent: change from baseline in domain scale scores and T-scores
 - Daily Activities
 - Mobility
 - Social/Cognitive
 - Responsibility
- Gait, using gait analysis by computerized mat during 6MWT: change from baseline in the following measures:
 - Stride Length
 - Base of Support

- Double Support
- Velocity
- Cadence
- Visual motor integration using the Beery-Buktenica Developmental Test of Visual Motor Integration (Beery-VMI) for subjects between 2 and 18 years of age: change from baseline.
- Spatial understanding and abstract reasoning using the Raven's Coloured Progressive Matrices (RCPM): change from baseline in total score

4.4 Safety Endpoints

The following endpoints will be used to evaluate the safety of UX007:

- Treatment emergent adverse events (TEAEs) including treatment emergent serious adverse events (TESAEs), fatal AEs, TEAEs leading to discontinuation, treatment related TEAEs and treatment related TESAEs
- Gastrointestinal (GI) TEAEs categorized using the standardized MedDRA query (SMQ) as listed in [Appendix C](#)
- Clinically significant changes from baseline in the following:
 - Vital signs and weight
 - Physical examination and ECG findings
 - Clinical laboratory evaluations
 - Pregnancy testing/pregnancy of partner
 - Suicidal ideation and behavior assessments
 - Concomitant medications
- Drug concentration measurements and bioassays
 - Plasma peak levels of UX007
 - Plasma levels of UX007 metabolites: C4 ketone (BHB), C5 ketones (beta-hydroxypentanoate [BHP]), and heptanoate
 - Non-fasting BHB
 - Trough UX007 and metabolites

4.5 Covariates

Covariates that may be incorporated into models include an appropriate associated baseline value and an indicator for whether a subject is an Absence Seizures Only Subject. Transformations will be considered for model covariates that are overly skewed.

4.6 Subgroups

Subgroup analyses will be done based on the derived seizure variables at baseline (see Section 5.6).

5 DEFINITIONS

5.1 Baseline

Baseline observable seizure frequency (see Section 5.7.1) from the seizure diary will be derived by measuring over approximately 6 weeks between the screening visit and the day prior to the randomization visit.

For all other measures, baseline value will be the last non-missing assessment prior to or on the date of the first dose of investigational product.

The baseline value will be used for all analyses of changes from the randomization visit and the phrases “change from baseline” and “change from randomization” will be used interchangeably.

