5.7.2 Absence Seizure Frequency

The absence seizure frequency from EEG (normalized to a 24-hour rate) is defined as

$$\text{Absence Seizure Frequency} = \frac{\text{Total number of absence seizures}}{\text{Number of hours observed}} \times 24$$

See Section 5.7.6 for the list of absence seizure types that are counted. Absence seizure frequency at baseline is measured at the randomization visit. Absence seizure frequency at 8 weeks is measured at the week 8 visit (Visit 5).

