7 DATA HANDLING AND ACCEPTANCE

7.1 Handling of Missing and Incomplete Data

Missing clinical outcome data can occur for multiple reasons, including missed subject visits and scales or measures with missing item scores. Missing and incomplete data will be identified through a review of tables and listings for this study. Missing and incomplete data will be identified for investigation and possible resolution by Data Management prior to the study database lock.

Unless otherwise specified, for missing assessments for an individual subject, these data would remain as missing. When a change from baseline is assessed, only subjects with a baseline and at least one post baseline measurement will be included in the analysis.

For primary and secondary analyses related to reduction in seizures from baseline to Week 8, imputation will be used to enable inclusion in analyses of all subjects in the Efficacy Analysis Set, the Efficacy Analysis Set – Observable Seizures and the Efficacy Analysis Set – Absence Seizures.

- For observable seizures subjects who have incomplete diary data during the Baseline Period but at least one day complete, observable seizure frequency will be calculated by averaging over the days with complete diary data. The same rule will be used for the Double-Blind Placebo-Controlled Treatment Period. Note that this also applies to subjects who terminate early.
- For absence seizures subjects who have incomplete EEG at either Randomization or Week 8, absence seizure frequency will be calculated by averaging over the time that is complete, even if the EEG is not done overnight.
- For subjects who have completely missing data for either Randomization or Week 8, a reduction from baseline in the natural logarithm of seizure frequency (+ 1) value of zero will be imputed for the response variable in any analyses of reduction from baseline, and non-response will be imputed for the response variable in any analyses of seizure response. For subjects who have completely missing data for Randomization, the Week 8 value will be imputed if available for the baseline covariate; if both Randomization and Week 8 are missing then the average baseline value of the subjects with complete data in the same treatment group will be imputed for the baseline covariate. In additional analyses related to reduction in seizures, two alternate methods will be implemented:

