DE = Dose Exploration Period. Visits DE-1 (Week 31) and DE-2 (Week 36) (± 3 days) apply only to subjects who participate in the Dose Exploration Period.

¹ Assessments at Week 2 will be completed via telephone call; no visit to the study site will be required. Subjects will return to the clinic at Week 4 and at the end of the double-blind Treatment Period for Week 8 (± 3 days). Visits during the Extension period will occur at 6-13 week intervals (± 2 weeks).

² Medical history includes subject demographics and Glut1 DS diagnosis confirmed by *SLC2A1* mutation analysis.

³ The seizure diary should be completed each study day, even on study days without seizures. Site personnel should help ensure that participants (parents/caregivers) are not leaving any blank pages in the seizure diaries.

⁴ All neuropsychological tests and assessments should be performed after the consumption of food and, as indicated, study drug. PPVT, Beery-VMI, RCPM, PEDI-CAT, and GMFM-88 will be administered at select sites only.

⁵ The 6MWT will include assessments of PED; a subset of sites may also perform gait analysis using a computerized portable walkway. Portions of the 6MWT, gait analysis and the GMFM-88 tests may be videotaped to monitor administration technique and assess qualitative changes in function. Subject identity will be protected by blurring out the facial area in the video.

⁶ CGI-S will be assessed at Baseline (Week 0); CGI-I will be assessed at Weeks 8, 26, 31, 36 and 52 (or Early Termination).

⁷ Confirmatory EEG at Screening for patients with absence seizures only is required for ~3 hours. For Week 0 EEG, begin EEG PRIOR TO Randomization date (requires 2-day visit); Week 8, 26, and 31 visits require a 2-day overnight visit to complete EEG. Monitoring periods of less than 12 hours in duration for Week 8, 26, and 31 visits will be considered a protocol violation.

⁸ At the Screening and Randomization Visits, a non-fasting blood sample will be drawn to assess non-fasting BHB. At subsequent post-randomization visits, blood samples for UX007 and metabolites will be drawn approximately 90 min following consumption of food and study drug. At Week 26, 3 blood samples will be drawn: pre-dose (within 15 min), and 2 additional timepoints at 60 and 180 min following consumption of food and study drug.

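### With a missing Week 0 EEG, the SAP's general baseline rule (5.1) is not reconciled with its EEG-specific rules (5.7.2, 8.6.3, 7.1), and 7.1 uses the Week 8 outcome as a baseline covariate

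*SAP*

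**What the plan says.** Four places in the SAP bear on a subject with no usable EEG at Week 0.

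- **SAP 5.1** carves out only diary seizure frequency. For everything else, "baseline value will be the last non-missing assessment prior to or on the date of the first dose". EEG falls under this general rule.
- **SAP 5.7.2** is specific to EEG: "Absence seizure frequency at baseline is measured at the randomization visit". It states no fallback. **SAP 8.6.3** likewise bases the absence measure in the primary endpoint on the overnight recordings at randomization and Week 8.
- **SAP 7.1** covers data that are completely missing at Randomization or Week 8. For the outcome, "a reduction from baseline in the natural logarithm of seizure frequency (+ 1) value of zero will be imputed for the response variable", with non-response imputed for responder endpoints. For the covariate when Randomization is missing, "the Week 8 value will be imputed if available for the baseline covariate"; and "if both Randomization and Week 8 are missing then the average baseline value of the subjects with complete data in the same treatment group" is used instead.
- **SAP Appendix B** shows that an earlier EEG can exist: "Confirmatory EEG at Screening for patients with absence seizures only is required for ~3 hours". Appendix A lists Screening among the EEG timepoints for the primary and absence endpoints.

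The EEG supplies the primary endpoint only for Absence Seizures Only Subjects (SAP 4.1 and 8.6.3). It also supplies the secondary endpoints of absence frequency and absence response. It is used for all Absence Seizures Subjects in the alternate derivation listed among the additional analyses in 8.6.3.

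**The concern.** Two things are wrong. First, the SAP does not say whether data count as completely missing for Randomization before or after the general rule in 5.1 has looked back to Screening. If after, the subject has a baseline and an observed change. If before, the subject has an imputed zero and an imputed covariate. Two programmers working from the same SAP could produce different primary and responder results.

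Second, the covariate fill in 7.1 uses the Week 8 value. That value is the outcome and treatment can change it, so it should not stand in for a pre-treatment covariate in an ANCOVA.

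The gap can arise in practice. Seizure eligibility under inclusion criterion 4 rests on the diary or the Screening EEG, not on the Week 0 EEG, and 7.1 itself provides for the missing case.

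**Working it through.** **Design figure.** With 30 UX007 and 10 placebo subjects (3:1 of 40), difference 50, SD 55 and one-sided alpha 0.05 (SAP 3.3, 3.5): SE = 55 × √(1/30 + 1/10) = 20.08; 50/20.08 = 2.49; 2.49 − 1.645 = 0.845; power = 0.801 (exact t: 0.788). This matches the stated 80% or so and is not in dispute. It fixes the arm sizes used below.

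**One subject, two routes.** Assume 40 absence seizures per 24 h at Screening, no Week 0 EEG, and 20 per 24 h at Week 8. These counts are illustrative; the documents give none.

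| | SAP 5.1 route | SAP 5.7.2 / 7.1 route |
|---|---|---|
| Baseline covariate | ln(41) = 3.71 | ln(21) = 3.04, the Week 8 value |
| Response | ln(41) − ln(21) = 0.67 | 0 by imputation |
| Percent reduction | 100 × (40 − 20)/40 = 50% | not computed |
| Responder (at least 50%) | yes | no, by imputation |

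One such subject is 1/10 = 10% of the placebo arm or 1/30 = 3.3% of the UX007 arm.

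**Effect on the estimate.** A log-scale ANCOVA was simulated with 30 versus 10 subjects and 3,000 runs per cell. All other inputs are assumptions: between-subject log SD 1.2, within-subject log SD 0.7, Screening EEG noise 1.4 times larger, true log effect 0 or ln 2 = 0.693, and 1 to 8 Week 0 EEGs missing at random. Every subject is treated as EEG-measured and the seizure-type covariate is omitted, so the exposure is larger than the primary analysis would have. Mean estimates with true effect 0.693:

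| Missing of 40 | 5.1 (Screening) | 7.1 (Week 8 covariate, response 0) | Response 0, true baseline covariate | Complete case |
|---|---|---|---|---|
| 1 | 0.699 | 0.671 | 0.669 | 0.700 |
| 2 | 0.697 | 0.665 | 0.660 | 0.694 |
| 4 | 0.701 | 0.646 | 0.625 | 0.692 |
| 8 | 0.690 | 0.580 | 0.559 | 0.696 |

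- *Choice of route.* The 7.1 estimate is lower than the 5.1 estimate by (0.699 − 0.671)/0.699 = 4% with 1 missing and (0.690 − 0.580)/0.690 = 16% with 8 missing.
- *Source of the loss.* With the true baseline as covariate and only the response set to zero, the loss is the same or slightly larger. The attenuation therefore comes from the zero response.
- *Effect of the Week 8 fill itself.* Relative to the true covariate, the table gives shifts of 0.002, 0.005, 0.021 and 0.021 towards UX007, with simulation noise. Fitting the covariate choices to the same simulated trials (8,000 per cell, same inputs) gives 0.004, 0.009, 0.017 and 0.030. A mean over both arms stayed within 0.004 of the true-covariate result in that comparison.
- *Same-arm mean versus both-arms mean.* When Week 8 is also missing, the estimates were 0.672, 0.666, 0.627 and 0.551 against 0.677, 0.660, 0.618 and 0.553. The largest gap is 0.009, which is within noise.
- *Type I error.* With no true effect, one-sided rejection was 0.045 to 0.059 under every rule, with simulation error of about ±0.008.

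**The case against.** The best defence is that the specific text governs the general. SAP 5.7.2 defines the absence baseline, 8.6.3 repeats it for the primary endpoint, and 7.1 says what to do when it is missing. A recording of about 3 hours at Screening is neither overnight nor at randomization, so the 5.1 route is already displaced. This is a sensible reading, but the SAP does not state it. SAP 5.1 excludes only the diary, Appendix A lists Screening as an EEG timepoint for the primary endpoint, and 7.1 accepts recordings that are not overnight.

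A second defence is that the reach is small. The Week 0 EEG is scheduled before randomization, and partial recordings are averaged, so only a completely missing one triggers the rule. The routes also diverge only if a Screening EEG exists, which is required only for patients with absence seizures only. This limits the size of the problem and stands.

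A third is that complete-case tables are prespecified. They help with the covariate fill, but they do not settle the conflict: who counts as complete depends on the same unanswered question. The primary-analysis code in Appendix D is redacted, so it may or may not resolve the derivation.

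A reader might also infer that the SAP holds three mutually conflicting rules, or that both fills bring treatment-affected values into the covariate. Neither follows. SAP 5.7.2 and 7.1 are compatible, and the Week 8 and arm-mean fills are ordered steps of one rule. The arm mean averages baseline values, so it depends on assigned arm but treatment cannot affect it.

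**Conclusion.** The point holds as a drafting gap plus one poor covariate choice. SAP 5.1 is not reconciled with 5.7.2, 8.6.3 and 7.1 for a subject with no Week 0 EEG, and the routes can give that subject a different change and a different responder status. The Week 8 fill is a post-treatment value used as a baseline covariate.

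It is tempting to conclude that the ANCOVA loses its basis in randomisation or that the type I error is inflated. The documents do not support that, and the simulation showed no inflation. The covariate fill has only a small effect, at most about 0.03 on a true log effect of 0.693 with 8 of 40 missing. The larger loss comes from the zero response and runs towards the null. Replacing the same-arm mean is justified by keeping the fill blind to treatment, not by any measurable effect here.

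These sizes rest on assumed variances and missingness. The documents do not give the number of missing Week 0 EEGs, so the actual effect on this trial is unknown.

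One related gap is open. SAP 5.6 uses absence frequency at Randomization to classify subjects with fewer than 4 observable seizures per 4 weeks. When that value is missing, it is unclear whether the diary or the EEG supplies the primary endpoint.

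**What to change.** 1. In SAP 5.1, state that the EEG baseline is the Week 0 EEG. Say whether the Screening EEG of about 3 hours may replace it, and if so whether in the primary or only in a sensitivity analysis. Cross-refer to 5.7.2, 7.1 and 8.6.3.
2. In SAP 7.1, replace both the Week 8 and the same-arm covariate fills with a treatment-blind value: the mean over both arms within seizure type, taken on the log(frequency + 1) scale that the model uses.
3. State explicitly whether the zero response and the imputed non-response stay for subjects with a missing Week 0 EEG but an observed Week 8 EEG. Changing the covariate alone would not give a complete rule.
4. In SAP 5.6, state how a subject with no Week 0 EEG is classified.

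The cost is SAP wording only, with no new data. The downside is that the estimate may be slightly less favourable to UX007 than with the Week 8 fill.
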